## **2.12. DESCRIPTION OF STUDY PROCEDURES**

### **2.12.1. Right Heart Catheterization and Simultaneous Pressure and Doppler Flow Velocity Measurement**

The right heart catheterization is performed as a clinical standard of care procedure, routinely performed for diagnostic purposes in this disease population. The standard right heart catheterization is performed with a balloon tipped, flow-directed pulmonary artery catheter (Swan-Ganz catheter), inserted through a sheath in the internal jugular vein. As per standard clinical protocol, hemodynamic recordings of right atrial, right ventricular, and pulmonary artery pressures, in addition to cardiac output, are made at baseline, and then repeated following pulmonary vasodilator challenge with inhaled nitric oxide (iNO, which is part of the standard clinical right heart catheterization when assessing pulmonary hypertension).

As a part of this protocol the subjects may undergo an additional hemodynamic measurement using a micromanometer pressure catheter that will be inserted via the Swann-Ganz catheter distal port. The micromanometer catheter will record high fidelity pressure signals for the measurement of pulmonary arterial input impedance. Measurements with micromanometer will be made with simultaneous flow velocity from transthoracic echocardiographic ultrasound at baseline just prior to nebulized AIR001 administration and at the time of the final hemodynamic assessment (60 minutes after second dose). This portion of the study that involves the micromanometer instrumentation is expected to add an additional 5-10 minutes onto the approximate 4 hour procedure.

#### **Cardiac Output (CO)**

Cardiac output is the amount of blood pumped through the left ventricle of the heart in a time interval of one minute. There are a number of ways to calculate CO. Thermodilution and/or Fick cardiac index are 2 means which will be used for measuring CO for this protocol. The CO will be the average of the recorded CO collected.

#### **Cardiac Index (CI)**

Cardiac index is a measurement that relates the CO from the left ventricle in one minute to body surface area (BSA) therefore determining cardiac function to size of the individual. CI is calculated by  $CO/BSA$ .

### **2.12.2. Pulmonary Capillary Wedge Pressure**

Pulmonary capillary wedge pressure (PCWP) provides an indirect estimate of left atrial pressure (LAP). PCWP is measured by the balloon-tipped, multi-lumen catheter (Swan-Ganz catheter) while it is in a branch of the pulmonary artery. Just behind the tip of the catheter is a small balloon that can be inflated with air (~1 cc). The catheter has one opening (port) at the tip (distal to the balloon) and a second port several centimeters proximal to the balloon. These ports are connected to pressure transducers. When properly positioned in a branch of the pulmonary artery, the distal port measures pulmonary artery pressure and the proximal port measures right atrial pressure. The balloon is then inflated, which occludes the branch of the pulmonary artery. When this occurs, the pressure in the distal port rapidly falls, and after several seconds, reaches a stable lower value that is very similar to left atrial pressure (normally about 8-10 mmHg). The balloon is then deflated and pulmonary artery pressure can again be recorded. The same catheter can be used to measure cardiac output. Blood samples will be withdrawn from the tip of the wedged catheter at baseline (pre-dose), and at 15 minutes after each dose of inhaled nitrite (45 mg dose and 90mg).

### **2.12.3 Echocardiography**

Transthoracic echocardiograms will be completed to assess RV function by measures such as TAPSE as well as to assess the Doppler waveform of the pulmonary artery. The echoes will be completed pre-dose and after final dose. This is a noninvasive test.

#### **2.12.4. Percutaneous Oxygen Saturation and Methemoglobin**

The device (Masimo Rainbow SET® CO-Oximeter) selected for use in this clinical trial has been validated to provide accurate determinations of both SaO2 and methemoglobin levels under conditions of hypoxia and methemoglobinemia. Continuous SaO2 and methemoglobin monitoring will occur prior to study drug administration until 2 hours post-dose. Measurements will be recorded pre-dose, approx. 5, 15, 30 and 60 minutes after each dose of AIR001 and approximately 2 hours post last dose of AIR001.

#### **2.12.5. Pharmacokinetic (PK) Studies**

Pharmacokinetic studies will be performed on all subjects enrolled to measure the concentration of inhaled nitrite and its metabolites in blood. The evaluation of the relationship between dosage and blood concentrations, and the relationship between blood concentrations and pharmacologic effects will provide valuable mechanistic information about the effects of inhaled nitrite on cardiopulmonary hemodynamics in Subjects with Pulmonary Hypertension.

To determine the pharmacokinetic profiles of the inhaled nitrite, blood samples will be collected at pre-nitrite dosing and at the end of nebulization at the presumed peak nitrite concentration for each tolerated dosage time points; approximately 15 minutes post inhalation. Vital signs, blood pressure and pulse oximetry will be measured and monitored closely at each time points. Samples will be immediately centrifuged and frozen at -20°C until the time of analysis.

PK samples will be accurately recorded for the collection time. Covariate information, e.g., age, body weight, height, disease type, concomitant medications, laboratory values, etc., will be obtained at the study visit. This is expected to yield an information-rich data set through dense sampling, enabling better characterization of the PK relationship of inhaled nitrite in subjects with PAH.

#### **2.12.6. Laboratory Testing**

Peripheral blood samples will be evaluated for baseline and follow-up comparison purposes which include complete blood count with differential, platelets, electrolytes, glucose, BUN, serum creatinine, liver function tests, PT/PTT, and nt-ProBNP. Urine pregnancy test may be performed only on female of child-bearing potential on Day 0 and Day 1.

Screening lab samples may be collected and analyzed at UPMC laboratories or at outlying facility of subject's choice. Lab results will be added to research chart for comparison. All 30-day samples will be analyzed at UPMC Presbyterian laboratory with the exception of the ntPro-BNP which may be processed and analyzed through the Pulmonary, Allergy and Critical Care Medicine (PACCM) research lab.

Baseline laboratory results within 6 months of screen visit may be used as baseline comparison and will not be repeated for research purposes. Blood samples may be collected on study visit 1 if baseline screening results are deemed clinically significant and warrant repeat testing or inadvertently not collected at screen visit.

### **2.12.7. Additional Laboratory Testing**

Blood samples may be collected for Cyclic Guanosine Monophosphate (cGMP) concentration determination and platelet mitochondrial will be collected at the end of nebulization at the at pre dose and the end of the peak dose of nitrite may be collected. cGMP measurements will be made on mixed venous blood using PCW pullback samples and venous blood will be collected for platelet mitochondrial analysis. These de-identified blood samples will be sent to the research lab on the 12th floor BST for processing.

### **2.12.8. Specimen collection and management**

#### Specimen Collection / Documentation

At each sampling time, one mL of blood will be withdrawn and discarded to assure that the solution used to maintain catheter patency does not dilute the sample. Blood samples will be accurately recorded for the actual sample collection time. Each research PK sample will be labeled with subject's unique identifier, sample date, scheduled sample collection time, and actual sample collection time. Covariate information, e.g., age, body weight, height, disease type, concomitant medications, laboratory values, etc., will be obtained at each time point. This is expected to yield an information-rich data set through dense sampling, enabling better characterization of the biomarkers in this patient population.

#### Specimen Handling and Labeling (De-Identification)

Specimens collected will be properly labeled. All research biological specimens and all records associated with the samples will be labeled only with a unique code that contains no personal identifiers. The information linking these code numbers to the corresponding subject's identity will be kept in a secure location in the investigator's office, and will not be available to staff managing samples at the research laboratories.

Immediately upon receipt of the biological specimens, all attempts will be made to process, isolate, collect, and store the specimens. The code number and date on which the specimen is frozen, all other information about the specimen, and subsequent processing will be entered on the specimen processing worksheet.

#### Specimen Management and Storage

Specimens in excess of immediate assay requirements may be stored indefinitely in a locked freezer under the control of the principal investigator.

The blood samples will be stored after appropriate coding to remove patient identifiers. The coding information linking patient identifiers to the stored samples will be maintained in a locked, secure area that will be accessible only to the study investigator. Subjects may request to have their samples destroyed at any time. These samples will be destroyed immediately upon receipt of the subjects' written request to do so. Identification of which samples to destroy will be available from the coding information linking patient identifiers to the stored samples as described earlier in this paragraph.

#### Restrictions to Direct Access of Specimens

Specimens will be kept in the responsible study investigators' laboratories indefinitely and will be under the control of the principal investigator. Investigators or other personnel not involved with the management or operations of the study are not permitted direct access to the specimens.

## **2.13. ENDPOINTS**

### **2.13.1. Primary Endpoints**

The primary outcome measures for this study is change in pulmonary vascular resistance (PVR) measured by right heart catheterization from time zero compared with peak effect within 60 minutes post completion of nebulized dose of nitrite.

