	
This is a single-center, open label phase II study to evaluate the effect of inhaled nitrite delivered in a dose escalation manner on the change in pulmonary vascular resistance (PVR) in subjects with pulmonary arterial hypertension undergoing right heart catheterization.
 
A total of 50 subjects with a confirmed diagnosis of pulmonary hypertension and meeting all inclusion/exclusion criteria will be enrolled in the study which will entail a single right heart catheterization. The study population consisted of subjects with WHO group I PAH (n=20), WHO group II PH (n=20) and subjects with WHO group III PH (n=10) will receive the dose escalation paradigm:
 
 
• Each subject will receive a starting dose of 45 mg inhaled nitrite (AIR001 Inhalation Solution), followed by a second dose of 90 mg inhaled nitrite, based on safety and tolerability.
 

The study visit will occur on the same day subjects are scheduled for their clinically indicated right heart catheterization or who volunteer for a research right heart catheterization for this specific study. Subjects on oral background PAH therapy (ETRA or PDE-5I) will be instructed to hold their regular PAH regimen on the day of the study visit.

Baseline pulmonary artery hemodynamic assessment, echocardiogram, micromanometry measured simultaneous pressure and flow velocity signals will be performed prior to inhaled nitrite treatment. Responses to 40 ppm inhaled NO will be measured before nitrite nebulization via a non-rebreather face mask to assess baseline, pre-AIR001 vasodilator responsiveness.

Subjects will receive a starting dose of 45 mg (placed in the nebulizer cup) of inhaled nitrite (AIR001), with one subsequent planned dose of 90 mg of inhaled nitrite, based on safety and tolerability, approximately 60 minutes after the first dose. During the study, right heart/pulmonary artery hemodynamics will be measured continuously, and cardiac output measured at 15 minute intervals, as well as noninvasive systemic blood pressure monitoring. Subjects will be tested for the changes in hemodynamics and calculated pulmonary vascular resistance (PVR) with inhaled nitrite.

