#### Pre-Dose: Baseline

- Physical examination to include vital signs, blood pressure, weight and oxygen saturation
- Laboratory testing that clinically warrants repeating testing or inadvertently not collected for screening may be obtained prior to research procedures
- Echocardiogram
- Non-invasive blood pressure measurement
- Right Heart Catheterization (RHC)-RA, RV, PA, pulmonary capillary wedge pressure (PCWP), CO/CI
- Inhaled NO testing at 40 ppm if PCWP < 25 with hemodynamic response recorded (RA, PA, PCWP, CO/CI)
- Micromanometry to record high fidelity pressure signals with simultaneous flow velocity from transthoracic echocardiographic ultrasound for the measurement of pulmonary arterial input impedance. Micromanometer pressure catheter is inserted via the Swann-Ganz catheter distal port.
- Repeat 2nd baseline hemodynamic measurement: RA, RV, PA, PCWP. CO/CI
- Pre-dose baseline PK, cGMP and platelet mitochondrial samples
- Pre-dose methemoglobin measurement

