#### AIR001 Dose 2 90mg Nebulized

- Non-invasive blood pressure measurement
- PK, cGMP and platelet mitochondrial samples (approx. 15 minutes after nebulization)
- RA, PA, PCWP, CO/CI (approx. 15, 30, 45, 60 minutes after nebulization)
- AE assessment
- MetHgb measurements (approx. 5, 15, 30, 60 minutes after nebulization)

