### **2.13.2. Secondary Endpoints**

The secondary endpoints measure:

- Time to maximum PVR decrease;
- Repeated measures ANOVA (RM-ANOVA) for change in PVR calculated from the start of inhalation and at times 15, 30, 45 and 60 minutes post end of nebulization.
- Change in mean pulmonary artery pressure, transpulmonary gradient and cardiac output (CO)/cardiac index (CI),
- Change in systemic blood pressure,
- Change in SVR, RV systolic (dP/dtmax/IP, PWRmax/EDV, RV EF, TAPSE), RV diastolic function (dP/dtmin, Tau),
- Changes in pulmonary vascular impedance / Wave Intensity,
- Change in plasma nitrite concentrations, cGMP, and platelet mitochondrial activity in mixed venous blood at specified time-points,

Change in pulmonary artery occlusion (capillary) pullback nitrite and plasma cGMP at baseline compared with both nitrite doses.

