## 2.15 STATISTICAL ANALYSIS

### 2.15.1 Sample Size and Power

Limited data are available on expected vasodilatory responses to nitrite in patients with Group I PAH or Group III PH. We reviewed data from studies examining the PVR response to inhaled NO, fasudil, iloprost, and treprostinil, which reported percent decreases in PVR after therapy ranging from 5-25%. Assuming a distribution of PVR among PAH patients similar to that reported by Voswinckel, et al (911 +/- 102 dyn·sec·cm^-5), we estimate using the paired t-test that we will need 14 participants to achieve 80% power to detect a statistically significant 10% decrease in PVR at a significance level of 0.05. At a projected enrollment of approximately 20 patients with group I PAH for our primary outcome measure, we anticipate more than sufficient power to detect significant acute vasodilatory effects of nitrite.

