### 2.15.2 Statistical Analysis

#### General Approach

The primary efficacy outcome variable is pulmonary vascular resistance (PVR), measured by right heart catheterization. T-test will be performed to determine difference of mean values for outcome variables at baseline and highest tolerated nitrite. The secondary endpoints will be analyzed with repeated measures ANOVA (RM-ANOVA) to compare the overall cardiopulmonary hemodynamic effects and the PK endpoints (eg: AUC) for all doses of nitrite.

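### The primary endpoint's peak effect is undefined; read naturally as each patient's lowest post-dose PVR, the planned t-test finds a fall far too often when nitrite does nothing.

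*Combined protocol and SAP*

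**What the plan says.** Section 2.13.1, and the synopsis in the same terms, defines the primary outcome as the change in PVR "measured by right heart catheterization from time zero compared with peak effect within 60 minutes post completion of nebulized dose of nitrite". The readings available after each dose are "RA, PA, PCWP, CO/CI (approx. 15, 30, 45, 60 minutes after nebulization" (section 2.10.2). No section says whether the peak is each patient's lowest value, a fixed time, or the time at which the group mean is lowest. The nearest guide is the first secondary endpoint in section 2.13.2, "Time to maximum PVR decrease", which is a quantity found patient by patient.

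Section 2.15.2 gives the primary analysis: "T-test will be performed to determine difference of mean values for outcome variables at baseline and highest tolerated nitrite". This settles the dose but not the time point. Section 2.15.1 sizes the study on an ordinary paired change: "we estimate using the paired t-test that we will need 14 participants to achieve 80% power".

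The design is open label, and all subjects follow the same 45 mg then 90 mg sequence (sections 2.1 and 2.2.1). Time zero is not tied to either of the two baselines listed in section 2.10.2: the first catheterization set, and a repeat "baseline hemodynamic measurement: RA, RV, PA, PCWP. CO/CI" taken after the nitric oxide challenge.

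**The concern.** A paired t-test asks whether the mean difference is zero. If the post-dose value is the smallest of four readings and the baseline is a single reading, the expected difference is below zero even when PVR never changes. Zero is then the wrong null value. In a controlled trial the same selection would act on both arms and largely cancel; here there is nothing to subtract.

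Two things are at stake. The 5% error rate of the primary test would not hold, so a significant result could not by itself show that nitrite lowers PVR. The estimated fall would also be too large, which matters because the study is meant to prepare larger trials.

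**Working it through.** **Inputs from the documents.** Four readings per dose at 15, 30, 45 and 60 minutes; nebulization of about 10 to 15 minutes (section 2.7.4); the second dose given "with one subsequent planned dose of 90 mg of inhaled nitrite, based on safety and tolerability, approximately 60 minutes after the first dose"; PVR 911 +/- 102; design effect 10%; significance level 0.05 (taken as two-sided); 14 patients required and about 20 planned in Group I (section 2.15.1). **Not in the documents:** the within-patient correlation and the reading-to-reading SD. Both are varied below.

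**1. The plan's own sample size.** The effect is 0.10 × 911 = 91.1. If 102 is the SD of the paired change, 12 patients give 80% power and 14 give 87%. If 102 is the SD at each time with correlation r, the SD of the change is 102 × √(2(1 − r)). At r = 0.40 this is 102 × √1.2 = 111.7, and 14 patients give 80.5%. So 14 is reproducible, but the calculation assumes a change centred on zero when the drug does nothing.

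**2. Independent readings, by formula.** Let σ be the SD of one reading. The lowest of four independent normal readings has mean −1.029σ and variance 0.492σ². Minus an independent baseline, the difference has mean −1.029σ and SD √(1 + 0.492)σ = 1.221σ.
- n = 20: 1.029/1.221 × √20 = 3.77. Against the critical value 2.093, a significant fall occurs in about 95% of trials.
- n = 14: 1.029/1.221 × √14 = 3.15, or about 83%.

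σ cancels, so the rate does not depend on how large the noise is.

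**3. Correlated readings, by simulation.** 20,000 trials per setting, no drug effect, first-order autoregressive noise in 15-minute steps, paired t-test of lowest-of-four minus baseline. The 90 mg readings fall 6–9 or 7–10 steps after baseline, depending on whether the 60 minutes run from the start or the end of the first nebulization. The 45 mg readings fall 1–4 or 2–5 steps after baseline. Entries are the rate of a significant fall; a valid test gives 2.5%.

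| Correlation per 15 min | 0 | 0.5 | 0.8 | 0.9 | 0.95 |
|---|---|---|---|---|---|
| 90 mg, n = 20 | 95% | 77–78% | 47–50% | 37–40% | 32–35% |
| 90 mg, n = 14 | 83% | 60% | 34–36% | 26–28% | 23–25% |
| 45 mg, n = 20 | 95% | 83–90% | 70–85% | 65–82% | – |

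The last row applies to patients who stop at 45 mg. Averaging the two pre-dose baselines does not help: 99%, 83%, 49% and 37% at correlation 0, 0.5, 0.8 and 0.9 (90 mg, 7–10 steps, n = 20).

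**4. A more favourable noise model.** Suppose the baseline and post-dose periods each carry their own shared shift, a fraction f of the within-patient variance, with the rest independent. The false fall is 1.029√(1 − f)σ and the SD of the difference is √(2f + 1.492(1 − f))σ. At f = 0.9 and n = 20: 0.325/1.396 × √20 = 1.04, a rate of about 16%. The rate is 64% at f = 0.5 and 29% at f = 0.8. It falls to about 10% at f = 0.95 and 6% at f = 0.98. At n = 14 and f = 0.9 it is about 12%.

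**5. Size of the false fall.** It is 1.03, 0.82, 0.55 and 0.40 reading SDs at correlation 0, 0.5, 0.8 and 0.9. If one SD is assumed to be 5–10% of PVR, this runs from 0.40 × 5% = 2% to 1.03 × 10% = 10% of PVR, against a design effect of 10%.

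**6. Other meanings of peak (n = 20).** One pre-named time, or the mean of the four readings, gives about 2.5% in each direction. Choosing the time from the group mean gives about 5–8% falls (6–8% in total).

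**The case against.** The strongest reply is that the inflation depends on a reading the plan does not state. Section 2.15.2 speaks only of mean values at baseline and at the highest tolerated dose, which would also fit a fixed time; time to maximum fall is a separate endpoint and does not define the primary one. That is fair, and the rates above are conditional on the per-patient reading. But no section names a fixed time. The presumed peak at about 15 minutes in the study treatment and PK sections refers to nitrite concentration for blood sampling, not to PVR.

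A second reply is that section 2.13.2 already includes "Repeated measures ANOVA (RM-ANOVA) for change in PVR calculated from the start of inhalation" and at the four fixed times. That analysis selects no minimum, but it is secondary and does not protect the primary claim.

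A third is that no lower bound on the error rate can be given without a known correlation. This stands: with a shared shift of 95% or more of the variance the excess becomes modest. It is also true that the group-mean reading is not clean, since 5–8% falls is two to three times the 2.5% expected in that direction. Neither point rescues the per-patient minimum.

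**Conclusion.** The concern holds and must be fixed before the primary result is interpreted. On the natural reading, the primary test at n = 20 in the 90 mg window declares a fall with no drug effect in about 32–95% of trials for correlations of 0.95 down to 0, and in about 16–64% if 90% down to 50% of the variance is a shared period shift. The valid figure is 2.5% in that direction. The exact rate is unknown because the documents give no within-patient correlation. The direction of the bias does not depend on it. The size of the false fall, about 2–10% of PVR, rests on an assumed reading SD of 5–10%. If peak meant one time fixed in advance, the test would be valid, so the missing definition decides whether the primary analysis can be relied on.

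**What to change.** Define the primary endpoint as the mean of the 15, 30, 45 and 60 minute PVR values after the highest tolerated dose, minus the repeat pre-dose baseline. State that this baseline is time zero, and name the paired t-test in section 2.15.2. If a short-lived effect is expected, name one time point in advance instead. Add a rule for a patient with a missing reading. Keep peak fall and time to peak as descriptive. Section 1.2 lists a comparison with inhaled nitric oxide (Aim 6) for which no analysis is given; if it is done, use the same non-selected nitrite value, because nitrite's peak would favour nitrite.

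The cost is wording only, since every reading is already scheduled. The mean answers a slightly different question and dilutes a brief effect. As an assumed example, take n = 20, a reading SD of 10% of PVR, and true falls of 10, 7.5, 5 and 2.5% at the four times (90 mg readings 7–10 steps after baseline, correlation 0 to 0.9). Power is about 57–73% for the mean and 85–99% for a pre-named 15 minute reading. With a sustained 10% fall the mean has 93–98%. At an assumed SD of 5%, all of these are about 99% or more. The choice between the two should follow the expected time course and be made before the data are seen.
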